3.10 Risk and benefit to study participants

As stated in the literature above, there are no serious side effects known to be caused by the investigational procedure. The study procedures are all routine procedures for the disease/condition studied. There is thus minimal risk for subjects.

This study may avoid radiation hazard and eliminates contrast-related hazards in already renal compromised patient. The equipment required is readily available. It can be accomplished in daycare setting, thus reducing the burden on theaters or catheter laboratories. It is instrumental in achieving rapid turnover with decreased in-hospital duration for patients.

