Fluoroscopy is used in the control group to assess for technical success. On table fistulogram visualization of less than 30% recoil of the target lesion signifies technical success. After a satisfactory result, a figure of 8 suture is placed with manual inflow occlusion. Post procedure, patients will be observed for any signs of haematoma or bleeding. If there are no immediate complications, patients will be discharged on the same day.

These procedures will be performed either by vascular surgeons or interventional radiologists below tabled:

OPERATOR	FISTULOPLASTY		CENTRE	DESIGNATION
	ULTRASOUND-GUIDED	FLUOROSCOPY-GUIDED		
[name] [name]	✓		University Malaya Medical Centre	Vascular surgeon
TBD		✓	University Malaya Medical Centre	Interventional radiologist
[name] [name]	✓	✓	Hospital Kuala Lumpur	Vascular surgeon

Cases with serious complications such as extravascular leak or significant pseudoaneurysm will be admitted for monitoring. If the complications are resolved then, the patient will be discharged. Follow-up may be scheduled earlier.

Follow-up will be done at two weeks, one month, three months and six months.

Assessment during follow-up includes:

- Resolution of symptoms (prolonged post dialysis bleeding or difficult access cannulation).
- Reduction of venous dialysis pressure to below predefined threshold values. (the acceptable value is less than 150mmHg)
- Measurement of the volume flow (the acceptable value is more than 500ml/min), flow characteristics (the acceptable characteristic is laminar flow) and diameter of the target lesion (the acceptable diameter is between 5-6mm) using duplex ultrasound.

[figure not shown]
In the event of a negative outcome during the first post fistuloplasty follow-up, it will be determined whether it is due to:

- a missed stenotic segment invisible to ultrasound or
- it is a case of severe stenotic segment refractory to fistuloplasty.

Patients belonging to the former category will cross-over to the fluoroscopic-guided fistuloplasty group. In the latter case, there is no reason to repeat the fistuloplasty regardless of the imaging method (ultrasound or fluoroscopy). Ideally, these particular patients should receive drug-coated balloon (DCB) fistuloplasty which is beyond the scope of this study. There is no alternative apart from switching to fluoroscopic-guided fistuloplasty.

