3.11 Risk Benefit Assessment

As stated above, there is minimal risk from the investigational study procedures. Study findings shall avoid radiation hazard and eliminates contrast-related hazards in already renal compromised patient. The expected benefit outweighs the minimal risk to subjects and thus this study should be supported. If any injuries do occur as a direct result of participating in the study, treatment for such injuries shall be provided.

Leskovar et al.³ reported 93% technical success with minor complications that were self-limiting and can be managed successfully by direct pressure. Complications include:

1. venous rupture (3.5%),
2. post-procedural thrombosis (1%),
3. balloon rupture with conversion to surgical procedure (0.5%),
4. guide wire false route (0.5%), and
5. pseudo-aneurysm at puncture site (0.5%).

Given that the intervention procedure is the exact same technique, as long as a minimum image quality is available, the outcome would essentially be the same for either imaging techniques. Complications arising from image quality would no longer matter.

In the case of **venous rupture**: tiny venous rupture of pseudoaneurysm can be managed by direct hand compression for 20 minutes and balloon occlusion or by placing covered stent. Extravascular leak or significant pseudoyaneurysm require emergency surgical repair.

Cases of **acute thrombotic occlusion** at access and plasty site can be managed successfully by giving additional heparin, thromboaspiration and over-the-wire Fogarty catheter.

Difficulty in recovering **ruptured balloon** requires either surgical removal or using ultrasound-guided snare.

We provide a comparison between the two visual modalities of fistuloplasty, as reported by Cho et al.⁴ in the table below.

NO.	COMPLICATIONS	FISTULOPLASTY		MITIGATION
		ULTRASOUND-GUIDED	FLUOROSCOPY GUIDED	
1	Vessel rupture	2/53 (3.8%)	1/90 (2.2%)	Successfully managed by balloon tamponade technique
2	Access thrombosis	1/53 (1.9%)	1/90 (2.2%)	-
3	Aneurysm development	-	1/90 (2.2%)	-
4	Sheath haematoma	-	1/90 (2.2%)	-

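### Section 3.10 says no serious side effects are known, but 3.1 and 3.11 describe serious complications and surgery; reconcile the wording and report complications by arm with exact intervals

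*Combined protocol and SAP*

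**What the plan says.** Section 3.10 states that "there are no serious side effects known to be caused by the investigational procedure", attributing this to the literature above it. It adds that "The study procedures are all routine procedures for the disease/condition studied" and concludes that risk to subjects is minimal. Section 3.11 opens by repeating the minimal-risk conclusion with a back-reference, and weighs the expected benefit against it.

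Three other statements bear on this:

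- **Section 3.1:** "Cases with serious complications such as extravascular leak or significant pseudoaneurysm will be admitted for monitoring".
- **Section 3.11, cited series:** an ultrasound-guided series is said to have had "minor complications that were self-limiting and can be managed successfully by direct pressure". The list that follows gives venous rupture 3.5%, post-procedural thrombosis 1%, balloon rupture converted to surgery 0.5%, guide wire false route 0.5% and puncture-site pseudoaneurysm 0.5%.
- **Section 3.11, management text:** "Extravascular leak or significant pseudoyaneurysm require emergency surgical repair".

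Comparing complication rates is the fourth specific objective in the synopsis and a secondary outcome in 3.1. Section 3.9 assigns the secondary objective to logistic regression, with P<0.05 as the threshold. No section defines or grades complications, and they are not among the follow-up assessments in 3.8.

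**The concern.** A statement that no serious side effects are known is factual. The same protocol names complications that it calls serious and says that some need surgery, so an ethics reviewer meets a premise in 3.10 that the next section undercuts. The benefit-risk conclusion in 3.11 leans on that premise.

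The analysis is affected too. The wording offers two labels for overlapping events, serious in 3.1 and minor in 3.11, and no definition settles which applies. Any split of complications by severity would then be decided after the data are seen. Serious events should also be few in a trial of this size, so a non-significant comparison could be read as confirming the favourable statement in 3.10.

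**Working it through.** **1. The sections side by side**

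| Topic | 3.10 | 3.1 | 3.11 |
|---|---|---|---|
| Serious complications | None known | Leak and significant pseudoaneurysm called serious | Cited complications called minor and self-limiting |
| Consequence of leak or significant pseudoaneurysm | Not mentioned | Admission for monitoring | Emergency surgical repair |
| Surgery in the cited series | Not mentioned | Not mentioned | 0.5% (balloon rupture) |
| Means of control | Not mentioned | Not mentioned | Direct pressure for the series; elsewhere covered stent, thromboaspiration, Fogarty catheter, surgical removal or snare |

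Two conflicts follow. Section 3.10 conflicts with 3.1 and 3.11 on whether serious complications are known. Section 3.11 conflicts with itself, because an event converted to surgery was neither self-limiting nor controlled by direct pressure. Sections 3.1 and 3.11 also state different consequences for the same two events, and these passages must be reconciled. The literature that 3.10 points back to (section 1) gives no complication rates for ultrasound guidance; the rates come afterwards, in 3.11.

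**2. The sample size, and what it was for**

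Section 3.6 uses 90% against 52.4%, power 80% and alpha 0.05 (two-sided assumed). With the pooled two-proportion formula and mean proportion 0.712:

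n = [1.96·√(2·0.712·0.288) + 0.8416·√(0.90·0.10 + 0.524·0.476)]² / 0.376² = (1.255 + 0.490)² / 0.1414 ≈ 21.6, so 22 per group, as stated.

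The final 27 is 22 × 1.2 = 26.4, rounded up (22/0.8 = 27.5 would give 28). The trial was sized on response, not on complications.

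**3. The listed rate tied to surgery**

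At 0.5% per patient, 27 ultrasound patients give 27 × 0.005 = 0.14 expected cases. The chance of at least one is 1 − 0.995²⁷ = 12.7%. No rate is given for extravascular leak or for pseudoaneurysm graded as significant.

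**4. What 27 per arm can show about complications**

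- Zero events, exact two-sided 95% upper limit: 1 − 0.025^(1/27) = 12.8%. With 22 evaluable it is 15.4%.
- Fisher's exact test, 5 against 0 of 27: 2·C(27,5)/C(54,5) = 2·80,730/3,162,510 = 0.051.
- Fisher's exact test, 6 against 0 of 27: 2·C(27,6)/C(54,6) = 2·296,010/25,827,165 = 0.023.
- With 22 per arm, 5 against 0 gives P = 0.048.

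**5. Whether logistic regression would work**

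The comparative study tabled in 3.11 gives vessel rupture as 2/53 (3.8%) under ultrasound. Under fluoroscopy it prints 1/90 beside 2.2%, but 1/90 is 1.1% and 2.2% would be 2/90, so both are used.

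- Chance of at least one rupture in 27: 64.9% at 3.8%, 45.2% at 2.2%, 25.8% at 1.1%.
- Chance that at least one arm has none: 1 − 0.649·0.452 = 71% (control 2.2%), or 1 − 0.649·0.258 = 83% (control 1.1%).

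With no events in one arm, ordinary maximum likelihood gives no finite odds ratio; with none in either, there is nothing to estimate. Rupture of any grade is the most frequent complication in the cited ultrasound series, so a serious subset would fare worse.

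**6. Size needed for a real comparison**

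The formula of step 2 gives about 1,784 per arm for 3.8% against 2.2%, and about 514 for 3.8% against 1.1%. Fisher's test at 27 per arm has power below 0.1% in either case.

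**The case against.** The strongest reply is that this is one loose sentence. The rates, their management and a two-modality table follow at once in 3.11, so nothing is hidden from an ethics reviewer. The sentence might also be meant to concern ultrasound guidance rather than fistuloplasty itself: 3.11 calls the technique the same under either imaging method, and its table shows rupture and thrombosis in both groups. The disclosure point stands and limits the harm. The narrower reading is possible, but 3.10 does not state it, so the sentence would still need rewriting.

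Several stronger readings are tempting, and the documents do not support them:

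- **That all rupture and thrombosis are serious.** Section 3.11 separates tiny ruptures from leak and significant pseudoaneurysm, and its table reports vessel rupture controlled by balloon tamponade.
- **That 3.1 lists rupture, conversion or emergency repair.** It lists none of these; they appear in 3.11.
- **That the listed rates measure serious risk.** The five rates add to 6.0% (about 1.6 events in 27), and the chance of at least one rupture in 27 is 62% to 65% at 3.5% to 3.8%. These figures cover complications of any grade.
- **That the routine label is contradicted.** A procedure can be routine for the condition while radiographic guidance is the usual practice at the two sites.
- **That 27 per arm was meant to support the risk statement.** Section 3.10 rests on literature and routine use.

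It is also fair that a minor label would not remove an event from an overall complication count. Only a split by severity is at risk.

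**Conclusion.** The concern holds as a contradiction of wording with a modest consequence for analysis. The 3.10 sentence is incompatible with 3.1 and 3.11, and 3.11 is inconsistent with itself on severity. Because the benefit-risk conclusion refers back to that sentence, it should be corrected. The only listed rate tied explicitly to surgery is 0.5%, or about a one-in-eight chance of at least one case in the ultrasound arm.

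A reader might infer that the minimal-risk judgement has been shown to be false. It has not: 3.10 gives no numerical risk, and the documents do not show that ultrasound guidance adds more than minimal risk.

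For the complication comparison, logistic regression will probably fail for rupture (71% to 83% chance of an empty arm), and a non-significant result would say little. This rests on cited rates applying per patient, 27 analysed per arm, independence between patients, and the logistic regression in 3.9 being meant to cover complications. The primary endpoint and sample size are unaffected.

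**What to change.** 1. Replace the 3.10 sentence with one that gives the complications and rates already cited in 3.11 and acknowledges that some are serious.
2. Reconcile the severity wording, and the stated consequences of leak and significant pseudoaneurysm, across 3.1, 3.10 and 3.11. The sponsor sets the grading, before data are reviewed.
3. Check that the patient information sheet agrees. Its text was not available here, so no fault in it is presumed.
4. In 3.9, for the complication objective, report the number and percentage of patients in each arm with any complication, and with a complication meeting the reconciled definition of serious. Give exact 95% confidence intervals and state the denominator. Do not rely on logistic regression for this objective.
5. State that a non-significant difference will not be reported as equal safety.
6. Correct the count or the percentage in the four cells of the 3.11 table that print 1/90 as 2.2%.

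The cost is protocol wording, possibly information-sheet wording, and one more table. The risk statement will read less favourably. No change to sample size, visits or the primary analysis is needed.

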3.11 Risk Benefit Assessment

As stated above, there is minimal risk from the investigational study procedures. Study findings shall avoid radiation hazard and eliminates contrast-related hazards in already renal compromised patient. The expected benefit outweighs the minimal risk to subjects and thus this study should be supported. If any injuries do occur as a direct result of participating in the study, treatment for such injuries shall be provided.

Leskovar et al.³ reported 93% technical success with minor complications that were self-limiting and can be managed successfully by direct pressure. Complications include:

1. venous rupture (3.5%),
2. post-procedural thrombosis (1%),
3. balloon rupture with conversion to surgical procedure (0.5%),
4. guide wire false route (0.5%), and
5. pseudo-aneurysm at puncture site (0.5%).

Given that the intervention procedure is the exact same technique, as long as a minimum image quality is available, the outcome would essentially be the same for either imaging techniques. Complications arising from image quality would no longer matter.

In the case of **venous rupture**: tiny venous rupture of pseudoaneurysm can be managed by direct hand compression for 20 minutes and balloon occlusion or by placing covered stent. Extravascular leak or significant pseudoyaneurysm require emergency surgical repair.

Cases of **acute thrombotic occlusion** at access and plasty site can be managed successfully by giving additional heparin, thromboaspiration and over-the-wire Fogarty catheter.

Difficulty in recovering **ruptured balloon** requires either surgical removal or using ultrasound-guided snare.

We provide a comparison between the two visual modalities of fistuloplasty, as reported by Cho et al.⁴ in the table below.

NO.	COMPLICATIONS	FISTULOPLASTY		MITIGATION
		ULTRASOUND-GUIDED	FLUOROSCOPY GUIDED	
1	Vessel rupture	2/53 (3.8%)	1/90 (2.2%)	Successfully managed by balloon tamponade technique
2	Access thrombosis	1/53 (1.9%)	1/90 (2.2%)	-
3	Aneurysm development	-	1/90 (2.2%)	-
4	Sheath haematoma	-	1/90 (2.2%)	-

3.12 Ethics of Study

The study will be conducted in compliance with ethical principles outlined in the Declaration of Helsinki and Malaysian Good Clinical Practice Guideline

Potentially vulnerable subjects (for example, pregnant and lactating women, children, prisoners, cognitively impaired and critically ill subjects) will be excluded from the study.

3.13 Informed Consent/Accent Process

Patients shall be informed of the study during their usual clinic visits. If they are interested, they will be briefed on it and given a copy of the Patient information sheet to read. If need be, they can take it home where they will be able to read through it properly and at leisure. No time limit is imposed. Once a patient agrees, an appointment will be made for him/her to meet with the principal investigator during which time the patient will again be briefed and given the opportunity to ask questions and to be clear about any remaining doubt. Given the patients willingness, the consent form will then be duly filled, signed and dated.

3.14 Privacy and Confidentiality

All information obtained in this study are subject to all applicable data security and confidentiality laws of Malaysia. As such, they will be treated in a manner respecting this fact. Your identity will thus be protected.

Raw data will be entered in hard copy data collection form. These will be kept safe at “Unit Rekod” of Hospital Kuala Lumpur and University Malaya Medical Centre.

The same data will be entered in a password-protected excel file in the Principal Investigator’s computer for the purpose of analysis. Identification numbers instead of patient identifiers will be used on subject data sheets. Upon completion of the study, soft copies of the data will be kept on CDs and erased from computer hard drives. Both soft and hardcopies of the data will be archived in the respective hospital record offices for a minimum of seven years after which, they will be destroyed.

Subjects will not be allowed to view their personal study data. Subjects can write to the investigators to request access to study findings.

3.15 Conflict of Interest

The investigators declare they have no conflict of interest.

3.16 Publication Policy

No personal information will be disclosed and subjects will not be identified when the findings of the survey are published.

Bacchini et al., ¹¹ 2000	USG-guided fistuloplasty	100	-	-
Karmota et al., ¹² 2020	Fluoroscopy-guided fistuloplasty	-	100	90

Appendix 2

Investigators	Study type	Intervention or comparison	n	Technical success
Ghanwat et al., ⁵ 2021	Prospective cohort study	USG-guided fistuloplasty	67	100%
Leskovar et al., ³ 2017	Prospective cohort study	USG-guided fistuloplasty	228	93%
Banerjee et al., ¹³ 2017	Prospective cohort study	USG-guided fistuloplasty	43	36/43 (84%)

Appendix 2

Investigators	Study type	Intervention or comparison	n	Technical success
Cho et al., ⁴ 2017	Case control study	USG-guided fistuloplasty vs conventional fistuloplasty	143	UG-PTA: 51/53 (96.2%); C- PTA: 84/90 (93.3%)
Wakabayashi et al., ⁶ 2013	Prospective cohort study	USG-guided fistuloplasty	2342	4288/4414 (97.1%)
Fox et al., ¹⁴ 2011	Prospective cohort study	USG-guided fistuloplasty	223	219/223 (98.2%)
Gorin et al., ⁷ 2011	Case control study	USG-guided fistuloplasty	31	-
Ascher et al., ⁸ 2009	Prospective cohort study	USG-guided fistuloplasty	32	-
Marks et al., ⁹ 2008	Prospective cohort study	USG-guided fistuloplasty	20	-
Kim et al., ¹⁵ 2007	Prospective cohort study	USG-guided fistuloplasty	45	10/10 (100%)
Marks et al., ¹⁰ 2007	Prospective cohort study	USG-guided fistuloplasty	10	100%
Bacchini et al., ¹¹ 2000	Prospective cohort study	USG-guided fistuloplasty	12	12/12 (100%)
Wittenberg et al., ¹⁶ 1996	Prospective cohort study	USG-guided fistuloplasty	39	38/39 (97%)
